10.7 Minimisation of Error and Bias

Selection bias will be minimized by a) the randomization process and b) consecutive enrolment of participants meeting inclusion criteria (and not meeting exclusion criteria). Study staff from all sites will be trained prior to study initiation in order to guarantee that inclusion and exclusion criteria and

This project is part of the EDCTP2 programme supported by the European Union

well understood and applied homogenously across sites.

Other potential sources of bias (ascertainment, information, interpretation), will be also addressed. Laboratory procedures will be standardized across sites, using the same laboratory SOPs and specific lab training, in order to minimize differences by site. Given that most tests are different by arm, and that AlereLAM will be preferably done at the health facility (by the bed side), no blinding of attending physician or lab technologist will be possible. In order to explore the differences between WHO recommended procedures and real standard of care at the sites, there is an exploratory objective aiming at assessing the current yield of TB investigations under routine conditions prior to the study initiation at all sites. This will be consecutive collection of retrospective data from PLHIV admitted at participating hospitals prior the start of the study. The quality and completeness of this data might differ from participating sites.

Decision to start TB treatment will be based on any test results and the criteria of the physician responsible for the patient's care.

10.8 Allocation to study arm

Enrolled patients will be randomly assigned to receive the diagnostic procedures specified for the intervention or control arm. Date and time of patient admission and recruitment need to be clearly recorded in the patient file (hour and when possible, minutes). Once the patient has provided the relevant baseline information specified above (recruitment section), the researcher will proceed to randomization and then, will open a patient file where the patient trial identification number will be clearly visible. A specific study card with study team contact information and patient study number will be handed to the participant.

The allocation of the study arm will be recorded in the participant study file under the appropriate CRF. Different coloured study files (to identify allocation) should be used. Patients could be recruited any day of the week although teams are encouraged to plan the relevant shifts over the weekend periods.

10.9 Arm-specific procedures (See table 2)

10.9.1 Intervention arm

The intervention arm for this trial will consist of testing sputum, stool and urine with Ultra and urine with AlereLAM in all recruited patients regardless of symptoms. Thus, all patients allocated to this arm will be asked to provide urine, stool and/or sputum.

This project is part of the EDCTP2 programme supported by the European Union

If urine or sputum cannot be provided spontaneously at the time of recruitment, participants will be asked to do so within 72 hours (aim: within 24 hours from enrolment). Patients will be encouraged to drink water to stimulate diuresis (unless contraindicated). Urine will be collected in specific containers and stored for future testing. Ultra on Stool will be performed in fresh specimen according to the KNCV SOS method³³.

Additionally, we will ask for stool and oral swabs specimen for Xpert Ultra/ LumiraDx testing.

We aim to collect all samples specified for each intervention (including those for exploratory studies) within 72 hours from enrolment. Efforts will be made to collect all samples within the first 24 hours. Time of sample collection will be specified in the sample collection log and CRF.

10.9.2 Control Arm

The control arm screening and testing strategy will consist of:

Sputum Ultra whenever the patient has cough, fever, weight loss or night sweats and/or *Ultra on any tissue* (including lymph nodes) from patients with suspected extrapulmonary TB.

Urine Alere TB-LAM, if patients 1) have signs and symptoms of TB (pulmonary and/or extrapulmonary), or 2) have advanced HIV disease* or 3) are seriously ill**. The latter two are all irrespective of signs and symptoms of TB.

*Adult patients with advanced HIV disease are those with CD4 cell count <200 cells/mm³ or a WHO clinical stage 3 or 4 event at presentation to the clinic.

**A seriously ill patient is any individual with HIV or of unknown HIV status presenting with one or more of the following danger signs:

- Unable to walk unaided
- A respiratory rate over 30/min
- A fever of more than 39°C, and/or
- A pulse rate of over 120/min

Thus, sputum and urine collection will only be conducted for Ultra and AlereLAM testing if the above-mentioned symptoms/criteria are present. Otherwise, urine alone will be collected in specific containers and stored for future testing. Patients will be encouraged to drink water to stimulate diuresis (unless contraindicated).

The control arm for this trial follows WHO recommendations (as of January 2020) for bacteriological testing among hospitalized HIV-positive individuals.

This project is part of the EDCTP2 programme supported by the European Union

Study staff will collect the samples for both arms.

In case any sample cannot be obtained within the first 72 hours from enrolment, reasons should be recorded in the appropriate CRF. In case the participant can provide the required sample(s) after 72 hours from enrolment, samples should still be collected and processed with clear indication of date and time. Special measures need to be implemented locally so the laboratory is aware of the tests to be performed despite some potential delay in specimen testing. After 72 hours from enrolment have passed, patient will be managed as per national guidelines.

Other than TB, patient clinical management will follow established national guidelines and protocols for hospitalized HIV-positive patients.

10.10 Follow up procedures (table 2)

Hospitalization stay (daily)

During hospitalization (daily) and at discharge, study team will verify and record whether a TB diagnosis has been made and/or anti TB treatment started. The study team will be working jointly with the routine health care staff so clinical decisions are made jointly. Study team will also record any ad-hoc TB investigation (additional Ultra, LAM testing, X-ray, etc) and their result. HIV care will follow national guidelines. .

Scheduled visits

After enrolment, there are two scheduled visits that need to take place unless the patient remains hospitalized (week 4 and week 8). These visits can occur either in the outpatient clinic, as home visits or by call or video-call depending on the patient and team preferences and COVID-19 epidemiologic situation. However, outpatient visits are recommended. A member of the study team will verify whether a TB diagnosis has been made on the relevant medical records (hospital or NTP office) and/or anti TB treatment started after discharge. Study staff will also record any ad-hoc TB investigation that was initiated by the care provider for clinical reasons (additional Ultra, LAM testing, X ray, etcetera) and their result (both by checking patient records and by asking the patient). HIV care will follow national guidelines. Vital status will also be recorded at these two visits. These visits will have a window period of -/+ 3 days (at week 4) and -3/+7 days at week 8.

In case a discharged participant does not attend the week 4 or week 8 visit, three phone call attempts will be made and, if unsuccessful, at least one home visit will be performed in order to collect relevant data to that visit. These attempts should be recorded in a patient tracking log. Week 4 visit should be sought until week 8 window visit opens, although will be considered a protocol deviation if done outside the week 4 window visit.

This project is part of the EDCTP2 programme supported by the European Union

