8.2 Secondary endpoints

- Eight-week all-cause mortality (main secondary endpoint) among all participants enrolled. The numerator will be number of deaths during eight weeks after enrolment, the denominator is the number of participants enrolled. We will compare this indicator between both study arms. In addition, this endpoint will also be calculated considering right censored observation when a participant is lost to follow up during the observation period or a

This project is part of the EDCTP2 programme supported by the European Union

participant experiences a different event that makes further follow up impossible.

- Time to TB treatment initiation among microbiologically confirmed cases and among all TB cases since enrolment. We will estimate Kaplan Meier curves (event= TB treatment initiation among laboratory confirmed TB patients and among all TB cases) and hazard ratios at day 7, 14, 28 and 56. Additionally we will compare the time to related estimates (mean and standard deviation) of intervention and control group.
- Proportion of cases re-admitted to hospital. The numerator will be the number of admissions after initial discharge and within 8 weeks from enrolment. The denominator will be the number of participants enrolled.
- The proportion of participants who are diagnosed with TB (irrespective of bacteriological confirmation) and started TB treatment within 72 hours of enrolment. The numerator is the number of participants diagnosed with TB (with or without bacteriological confirmation) who started treatment within 72 hours of enrolment; the denominator is the number of participants enrolled.
- The proportion of participants who are diagnosed with microbiologically confirmed TB and are started on treatment at 7 days, 14 days, 4 weeks and 8 weeks of enrolment. In addition, this endpoint will also be calculated considering right censored observation when a participant is lost to follow up or dead during the observation period or a participant experiences a different event that makes further follow up impossible.
- Proportion of participants who are able to provide sputum, stool and urine samples for Ultra/AlereLAM testing within 24, 48 and 72 hours of enrolment (the numerator is the number of urine samples or (and) sputum samples provided within 72 hours of admission and the denominator is the number of patients enrolled).

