10.11 Participant study completion (week 8)

Patients might terminate their participation in the study at any point. Reason, if available, should be recorded in the patient file. Once participants have completed their week 8 visit (at the hospital/outpatient clinic or as home visit), they will be considered having completed their participation in the study. For those not attending week 8 visit, they will be considered lost to follow up after the three phone call attempts and home visit have occurred. Deaths occurring during the study at patient's household will be documented and relatives will be asked about signs and symptoms before death. In settings where verbal autopsies are routinely conducted (CISM), this data will be considered a study source document and information captured in the off-study-form.

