13.2.2 Statistical methods

Variables will be summarized using descriptive statistical methods. Continuous data will be described using the mean and standard deviation statistics when these values follow the normal distribution. Otherwise we will use the median and interquartile range when we will not assume this distribution. Categorical values will be summarized using frequency and/or percentages.

For categorical comparisons we will use a Chi-square test or Fisher exact test according to the

This project is part of the EDCTP2 programme supported by the European Union

data characteristics. Likewise, the continuous comparisons will be tested by Student t-test, Anova test or Kruskal Wallis test.

When necessary, we will transform the continuous data, especially laboratory data, in non-linear scale. For these cases we will describe these data with geometric mean. Heterogeneity between sites will be analyzed.

Assessment of loss to follow-up as random across arms

We will analyze the baseline characteristics between lost and non-lost follow up patients and across arms to ensure that loss to follow up occurs randomly. If we find any significant attribute we will adjust the analysis by this/these factors.

Time-to-event data

Time-to-event data (such as time to mortality, time to TB diagnosis or time to treatment initiation (among lab confirmed or all TB)) will be presented using Kaplan-Meier curves with a log rank test (two-sided 0.05 significance level). The analysis of covariates on time-to-event data will be performed using a Hazard Ratios estimated through Cox regression models.

Comparisons between control and intervention arm will be established at prespecified time points (day 7, day 14, day 28 and day 56). Mean time (and SD) to event per study arm will also be estimated.

Significance levels

The significance level for most comparisons is $p=0.05$. For selected secondary endpoints measured at several timepoints and subgroup analysis, the significance level will be $p=0.01$

Study discontinuations & patient disposition

Patient disposition and reasons for premature discontinuations and their frequencies will be tabulated.

Datasets analyzed

Number of patients in each analysis set will be tabulated and listings of any patients excluded from any analysis set will be provided.

Efficacy analysis

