### 3.4 Endpoints

All study endpoints will be compared between control and intervention arm. Also, the final results will be presented disaggregated by sex.

3.4.1 The **primary endpoint** is the proportion of participants diagnosed with microbiologically confirmed TB and started on TB treatment within 72 hours of enrolment\* in whom TB is microbiologically confirmed\*/\*\*

\* The numerator of the primary endpoint includes participants per study arm who are diagnosed with microbiologically confirmed TB and initiated TB treatment within 72 hrs of enrolment. The denominator is the number of enrolled participants in each study arm.

\*\* Participants are defined to have microbiologically confirmed TB if at least one confirmatory TB test (Ultra, AlereLAM) gives a positive result.

**Secondary endpoints** are:

Related to main objective

3.4.2.1 Time-to-TB-treatment-initiation among microbiologically confirmed cases and among all TB cases since enrolment. We will estimate Kaplan Meier curves and hazard ratios at day 7, 14, 28 and 56. Additionally we will compare the time to related estimates (median and IQR) of intervention and control group.

3.4.2.2 Proportion of cases re-admitted to hospital. The numerator will be the number of admissions for any reason (not included in the exclusion criteria) after initial discharge and within 8 weeks from enrolment. The denominator will be the number of participants enrolled.

---

3.4.2.3 Proportion of participants who are diagnosed with TB (irrespective of bacteriological confirmation) and have started on TB treatment within 72 hours of enrolment.

3.4.2.4 Proportion of participants who are diagnosed with microbiologically confirmed TB and are started on treatment at 7, 14 days and 8 weeks of enrolment.

3.4.2.5 Time to laboratory confirmed TB diagnosis and any TB diagnosis since enrolment.

3.4.2.6 Proportion of microbiologically confirmed TB participants started on treatment without Rif resistance information (only AlereLAM positive)).

Related to secondary objectives.

3.4.2.7 Eight-week all-cause mortality. The numerator will be the number of deaths during eight weeks after enrolment, the denominator the number of participants enrolled.

3.4.2.8 In hospital and 4-week all-cause mortality among all participants enrolled (assessed as the eight-week all-cause mortality).

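### The week-8 visit may take place from day 53 and ends participation, so the crude 8-week proportions can miss a few events up to day 56; the effect is small and cheap to remove

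*Protocol*

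**What the plan says.** **Visit window.** Protocol 10.10: "These visits will have a window period of -/+ 3 days (at week 4) and -3/+7 days at week 8". Protocol 10.5 makes the day of randomization study day 0, and Protocol 13.2.2 takes day 56 as the last time point: "Comparisons between control and intervention arm will be established at prespecified time points (day 7, day 14, day 28 and day 56").

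**End of participation.** Under Protocol 10.11, once the week-8 visit is done, "they will be considered having completed their participation in the study". The telephone attempts and home visit in 10.10 and 10.11 are for people who do not attend, not for people who attend early.

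**Vital status.** After discharge it is tied to the week-4 and week-8 contacts: "Vital status will also be recorded at these two visits". The visit table adds daily verification for inpatients and a check at discharge.

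**Endpoint.** Protocol 8.2 names the main secondary endpoint: "Eight-week all-cause mortality (main secondary endpoint) among all participants enrolled". It defines it as a crude proportion: "The numerator will be number of deaths during eight weeks after enrolment, the denominator is the number of participants enrolled". SAP 3.4 agrees: "Eight-week all-cause mortality. The numerator will be the number of deaths during eight weeks after enrolment, the denominator the number of participants enrolled". Readmission within 8 weeks and confirmed TB with treatment started by 8 weeks are also proportions of participants. SAP 8.2.1, 8.2.3 and 8.2.5 compare these three proportions between arms.

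**Censored version.** Protocol 8.2 adds that "this endpoint will also be calculated considering right censored observation when a participant is lost to follow up during the observation period", or when another event prevents follow-up. Early completion is not named.

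**The concern.** Endpoint and data collection cover different periods. The endpoint runs to day 56, while a site that follows the protocol exactly may close a participant on day 53. What happens after that visit and by day 56 belongs in the numerator, but no one is asked to find out. In a proportion with all enrolled participants as denominator, such a person is recorded as alive, not readmitted and not newly treated.

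The error has one direction: the crude 8-week proportions can only be too low. It cannot be repaired at analysis, because the data do not exist. Week 4 is different, since a death after an early week-4 visit is found at week 8 and its date is recorded.

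**Working it through.** The plan states no figure for this loss, so there is none to reproduce. The calendar comes from the documents. The mortality inputs are assumptions, because neither document gives an 8-week mortality.

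**Calendar**
- Week 8: 8 × 7 = day 56.
- Window: 56 − 3 = day 53 to 56 + 7 = day 63, which is 11 permitted days. Three of them (53, 54, 55) come before day 56.
- Longest unobserved stretch: 3 days, or 3/56 = 5.4% of the endpoint period.

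**Missed deaths, assumed late hazard**

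Formula: missed deaths ≈ people alive × unobserved days per person × daily hazard.

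Inputs: 1172 enrolled (Protocol 13.1); assumed 80% alive at day 53, so 1172 × 0.8 = 937.6; assumed hazard 0.001 to 0.003 per day.

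| Visit pattern | Person-days unobserved | Deaths missed |
|---|---|---|
| All seen on day 53 | 937.6 × 3 = 2813 | 2.8 to 8.4 |
| One third seen early, 2 days unobserved each | 937.6/3 × 2 = 625 | 0.6 to 1.9 |
| Visits spread evenly over the 11 days | 937.6 × (3+2+1)/11 = 511 | 0.5 to 1.5 |

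In the second row the loss is 0.6/1172 to 1.9/1172, or 0.05 to 0.16 percentage points.

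**Check from assumed 8-week mortality**

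Formula: missed proportion = S(v) − S(56) for a visit on day v, with S(t) = exp{−λ(t/56)^k} and λ = −ln(1 − m). Here m is 8-week mortality, k = 1 is a constant hazard, and k = 0.5 is a hazard concentrated early.

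| m | k | All on day 53: points (deaths in 1172) | One third on day 54: deaths in 1172 |
|---|---|---|---|
| 10% | 0.5 | 0.26 (3.0) | 0.7 |
| 20% | 0.5 | 0.49 (5.7) | 1.3 |
| 30% | 0.5 | 0.68 (8.0) | 1.8 |
| 10% | 1 | 0.51 (6.0) | 1.3 |
| 20% | 1 | 0.96 (11.3) | 2.5 |
| 30% | 1 | 1.35 (15.8) | 3.5 |

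The k = 0.5 rows reproduce the first table, because their hazard at day 56 (kλ/56) is 0.09 to 0.32% per day. A constant hazard about doubles the numbers, but it assumes that people die as fast in week 8 as in the days after admission.

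Missed readmissions and treatment starts cannot be sized, since the documents give no rate for either.

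**The case against.** **Only part of the window and of the population is affected.** This stands. Visits on days 56 to 63 cover the full period, and people still in hospital are verified daily. It would be too strong to say that every day-56 estimate lacks follow-up by design.

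**Time-to-event analyses are not harmed in the same way.** This stands. A reader might infer that Kaplan-Meier and hazard estimates at day 56 fail because early attenders leave before that day. Censoring at last contact is what these methods are built for, and such people are not counted as survivors. Protocol 13.2.2 lists time to mortality among these analyses, and SAP 4.4 assigns death dates and the study-end date to the Kaplan-Meier graphs. The usual condition of non-informative censoring applies. None of this rescues the crude proportions in SAP 8.2.

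**Bias between arms is not shown.** This stands. A reader might suspect that, in an unblinded trial, visit timing differs by arm. The window is the same in both arms, and nothing in the documents points to different timing. A shared loss of one or two deaths barely moves the comparison.

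**The visit tables do not prove a second window.** The Protocol table shows a 3-day tolerance beside week 8, and the SAP copy shows it beside week 4. That is probably a cell displaced when the table was read from PDF, so no contradiction should be built on it. The lower limit is day 53 on either Protocol reading.

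**Ordinary loss to follow-up is larger.** The plan expects 5%, about 59 of 1172. This is true, but that loss is anticipated and pursued with calls and a home visit. The gap here arises in participants who were in contact with the study.

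**Conclusion.** The gap is real, and limited to discharged participants seen on days 53 to 55 and to the crude 8-week proportions for death, readmission and treatment start. In a plausible case about 1 to 2 deaths in 1172 would be missed. About 3 to 8 would be missed only if everyone were seen on day 53. These figures rest on an assumed late hazard of 0.1 to 0.3% per day with 80% alive. With a constant hazard and 10 to 30% mortality they rise to about 1 to 4 and 6 to 16. The crude proportions are too low by that amount; the documents give no reason to expect a distorted arm comparison. This is a cheap improvement, not a threat to the trial's conclusions. It is worth making because it completes the main secondary endpoint.

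**What to change.** Either of two changes closes the gap:
- set the lower limit for week-8 outcome ascertainment at day 56, for example 0/+7 days; or
- keep the present window and, for anyone seen on days 53 to 55, require a brief phone check of vital status, TB treatment start and readmission on or after day 56, before the Study Completion form is signed.

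In both cases, state in the SAP that events are counted by date up to and including day 56, so that events on days 57 to 63 learned of at a late visit stay out of the numerators. Use the same window in Protocol 10.10 and both visit tables.

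The cost is a window of 8 days instead of 11, or one short call for each early visit. Protocol 10.10 already allows the visit itself to be done by call, so no new procedure is needed.
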